**Table 9.4.4-1: Clinical Laboratory Assessments**

Hematology	
Hemoglobin	
Hematocrit	
Total leukocyte count, including differential	
Platelet count	
Blood type (ABO, Rh, and indirect antiglobulin testing) (screening only)	
Serum Chemistry	
Aspartate aminotransferase (AST)	Albumin
Alanine aminotransferase (ALT)	Sodium
Total bilirubin	Potassium
Alkaline phosphatase	Chloride
Lactate dehydrogenase (LDH)	Calcium
Creatinine a	Magnesium
Blood Urea Nitrogen (BUN) or serum urea level	Creatinine clearance (CLcr)- screening only
Glucose, Phosphate	Carbon Dioxide or Bicarbonate b
	Amylase and lipase: only for participants with pancreatic adenocarcinoma
Urinalysis	
Protein	
Glucose	
Blood	
Leukocyte esterase	
Specific gravity	
pH	
Microscopic examination of the sediment if blood, protein or leukocytes esterase are positive on the dipstick	
Thyroid Function Tests	
TSH (reflex to free T3 and free T4 if abnormal result)	
Serology	
Hepatitis B surface antigen (HBV sAg, Australia antigen), and hepatitis C antibody (HCV Ab) or HCV ribonucleic acid (RNA)HIV-1 and -2 antibody (screening only)	
Other Analyses	
Pregnancy test (WOCBP only: screening, predose, discharge).	
Follicle stimulating hormone (FSH) (screening only for women only)	

a Creatinine clearance measured by 24-hour urine collection or estimated from serum creatinine by the Cockcroft-Gault formula.

b To be done in sites where this is a standard part of the chemistry panel. In sites where testing for CO2/HCO3 is not standard, the test is optional.

#### **9.4.4.1 Blood Typing**

Blood Type, Rh factor, and Indirect Antiglobulin Test (IAT) should be done before the first dose of daratumumab. Participant RBC phenotyping (standard or extended) is an alternative option to the IAT test, if locally required. Either method must be completed prior to first daratumumab infusion. Daratumumab interferes with the IAT, which is a routine pre-transfusion test performed to identify a patient's antibodies to minor antigens so that suitable donor blood can be given for transfusion. Daratumumab does not interfere with ABO/RhD typing. CD38 is expressed at very low levels on erythrocytes. Daratumumab binds to the CD38 on erythrocytes, which results in a positive IAT (Indirect Coombs Test). This positive result masks the detection of antibodies to minor antigens and may prevent or delay blood banks from issuing donor blood for transfusion. This effect occurs during daratumumab treatment and for up to 6 months after treatment ends. Participants will receive a Participant Alert Card (PAC) for the study that includes the blood profile (ABO, Rh, and IAT or phenotyping) determined before the first infusion of daratumumab along with information on the IAT interference for healthcare providers/blood banks. Participants are to carry the PAC throughout the treatment period and for at least 6 months after treatment ends. Blood banks can eliminate the daratumumab IAT interference with IAT by treating reagent RBCs with dithiothreitol (DTT).

Possible methods for blood banks to provide safe RBCs for transfusion to participants receiving daratumumab include:

- a) Providing ABO/RhD compatible, phenotypically (standard or extended phenotyping) or genotypically matched units
- b) Providing ABO/RhD compatible, K-negative units after ruling out or identifying alloantibodies using DTT-treated reagent RBCs

Uncrossmatched, ABO/RhD compatible RBC units should be administered if transfusion is needed emergently as per local blood bank practice. Despite daratumumab binding to CD38 on erythrocytes, no indication of clinical significant hemolysis has been observed in daratumumab studies.

#### **9.4.5 Safety Assessment**

At baseline, a medical history will be obtained to capture relevant underlying conditions. The baseline examinations should include signs and symptoms, weight, ECOG Performance Status, BP, HR, temperature, and respiratory rate should be performed within 14 days prior to first dose except where noted in [Table 2.-1](#). Concomitant medications will also be collected within 14 days prior to first dose and through the study treatment and follow-up periods. (See [Table 2.-2](#) and [Table 2.-3](#)).

Baseline safety laboratory assessments should be done within 14 days prior to the first dose (see [Table 2.-1](#)). Pregnancy testing for WOCBP (done locally) to be done within 24 hours prior to first dose, and then every 4 weeks (+/- 1 week) regardless of dosing schedule, and at each safety follow up visit.

Determination of safety lab results is required prior to dosing. If there are delays with obtaining results for certain tests, please contact the medical monitor to determine clinical significance.

Participants will be evaluated for safety if they have received any study drug. Toxicity assessments will be performed continuously during the treatment phase. During the safety follow-up phase (see [Table 2.-3](#)) toxicity assessments should be done in person.

Adverse events and laboratory values will be graded according to the NCI-CTCAE version 4.

On treatment vital signs should be monitored extensively on Week 1 and 2 before, during, and after the first infusion of daratumumab as follows: immediately before the start of the infusion, at 30 minutes, 1 hour, 90 minutes, 2 hours, and 3 hours 30 minutes after the start of the infusion; at the end of the infusion, and 30 minutes, 1 hour, and 2 hours after the end of the infusion. For all other cycles, measure vital signs prior to administration of premedication of daratumumab, and pre-nivolumab and daratumumab and after the end of the infusion. The start and stop time of the nivolumab and daratumumab infusions should be documented. Physical examinations are to be performed at treatment visits as clinically indicated. If there are any new or worsening clinically significant changes since the last exam, report changes on the appropriate non-serious or serious adverse event page.

Additional measures, including non-study required laboratory tests, should be performed as clinically indicated or to comply with local regulations. Laboratory toxicities (eg, suspected drug induced liver enzyme elevations) will be monitored during the follow-up phase via on site/local labs until all study drug related toxicities resolve, return to baseline or are deemed irreversible.

Some of the previously referred to assessments may not be captured as data in the eCRF. They are intended to be used as safety monitoring by the treating physician. Additional testing or assessments may be performed as clinically necessary or where required by institutional or local regulations.

### 9.5 Pharmacokinetic

As of Revised Protocol 03, the collection of pharmacokinetic samples was discontinued.

[REDACTED]

**9.8.2 Immunogenicity Assessments**

As of Revised Protocol 03, the collection of immunogenicity samples is discontinued.

**10. STATISTICAL CONSIDERATIONS**

**10.1 Sample Size Determination**

Sample size determination is not based on statistical power calculation.

40 participants were to be enrolled to each cohort; enrollment to the NSCLC cohort was closed before this target was attained. In this study, an ORR in excess of 10% will be considered of clinical interest for TNBC and PAC cohort. An ORR in excess of 20% will be considered of clinical interest for NSCLC cohort.

Assuming the true ORR is 25%, 40 participants in each tumor type can provide approximately 79.8% power to reject the null hypothesis that the ORR is 10%, considering a 2-sided alpha of 5%.

Assuming the true ORR is 40%, 40 participants in each tumor type can provide approximately 83.7% power to reject the null hypothesis that the ORR is 20%, considering a 2-sided alpha of 5%.

Table 10.1-1 shows the precision of the estimation of ORR based on the two sided 95% exact CI using Clopper-Pearson methods based on 4, 8, 12, 16 and 20 responders out of 40 participants. At observed more than or equal to 9 responders, i.e.,  $ORR \geq 22.5\%$ , the lower bound of the 95% CI excludes 10%. At observed more than or equal to 14 responders, i.e.,  $ORR \geq 35\%$ , the lower bound of the 95% CI excludes 20%.

**Table 10.1-1: Two-sided 95% exact CI using Clopper-Pearson Method Based on the Number of Observed Responses from 40 participants**

Number of Observed Responses	4	8	12	16	20
Observed Response Rate	4/40 (10.0%)	8/40 (20.0%)	12/40 (30.0%)	16/40 (40.0%)	20/40 (50.0%)
95% exact CI (%)	(2.8, 23.7)	(9.1, 35.6)	(16.6, 46.5)	(24.9, 56.7)	(33.8, 66.2)

A sample size of 40 can also detect, with more than 87% probability, a safety event that occurs at an incident rate of 5%.

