### 10.3.1 Efficacy Analyses

Endpoint	Statistical Analysis Methods
Primary	NA
Secondary	
ORR as defined as proportion of participants who achieved a best overall response (BOR) of CR or PR before taking any subsequent anti-cancer therapy, will be computed in each cohort along with the exact 95% CI using Clopper-Pearson method.
 
BOR is defined as the best response designation recorded between the date of first dose and the date of the initial objectively documented tumor progression per investigator assessment using RECIST 1.1 criteria or the date of subsequent therapy, whichever occurs first
 
Duration of response (or complete response) in each cohort will be estimated using KM product-limit method for participants who achieve PR or CR (or CR only). Median values along with two-sided 95% CI will be calculated.
 
Investigator-assessed progression free survival (PFS) is defined as the time from first dosing date to the date of the first documented tumor progression, as determined by investigators (per RECIST 1.1), or death due to any cause. Participants who die without a reported progression will be considered to have progressed on the date of their death. Participants who did not progress or die will be censored on the date of their last tumor assessment. Participants who did not have any on study assessments and did not die will be censored on the randomization date. A participant who initiates a subsequent anti-cancer therapy will be censored on the date of last tumor assessment prior or on the start date of their subsequent anti-cancer therapy.
 
The PFS curve, median and PFS rate at appropriate time points for each cohort will be estimated using the Kaplan-Meier product-limit method. Two sided, 95% confidence intervals for median PFS will be computed by Brookmeyer and Crowley method. A two-sided, 95% confidence interval for the PFS rates will be computed by Greenwood method for variance derivation and on log-log transformation applied on the survivor function S(t).

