#### **10.3.4 Interim Analyses**

An interim analysis of futility is planned. For TNBC or PAC cohort, if 2 or less responders were observed among the first 20 participants after 4 months on treatment, the recruitment of the cohort will be assessed for potential stopping. If the true ORR is 10%, the probability of stopping the cohort is 68%. If the true ORR is 25%, the probability of stopping the cohort is 9%. At the time of interim analysis, disease control rate and duration of response, as well as progression free survival (PFS) will be also evaluated for each cohort. The stopping of the cohort for futility will be based on the totality of the evidence on efficacy.

Under the circumstance that data of some tumor types mature faster than others or a strong signal is observed in some tumor types, interim analyses may be performed prior to the completion of the study in order to facilitate program decisions such as expanding the current study or starting phase 3 development and to support presentations or publication. These interim analyses will not impact the study duration or enrollment completion, and the trial will continue as planned.

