5 SAMPLE SIZE AND POWER

Sample size determination is not based on statistical power calculation.

40 participants were planned to be enrolled to each cohort. In this study, an ORR in excess of 10% will be considered of clinical interest for TNBC and PAC cohort. An ORR in excess of 20% will be considered of clinical interest for NSCLC cohort.

Assuming the true ORR is 25%, 40 participants in each tumor type can provide approximately 79.8% power to reject the null hypothesis that the ORR is 10%, considering a 2-sided alpha of 5%.

Assuming the true ORR is 40%, 40 participants in each tumor type can provide approximately 83.7% power to reject the null hypothesis that the ORR is 20%, considering a 2-sided alpha of 5%.

Table 5.1 shows the precision of the estimation of ORR based on the two-sided 95% exact CI using Clopper-Pearson methods based on 4, 8, 12, 16 and 20 responders out of 40 participants. If at least 9 responses are observed, i.e., $ORR \geq 22.5\%$, the lower bound of the 95% CI excludes 10%. If at least 14 responses are observed, i.e., $ORR \geq 35\%$, the lower bound of the 95% CI excludes 20%.

Table 5-1: Two-sided 95% exact CI using Clopper-Pearson Method Based on the Number of Observed Responses from 40 participants

Number of Observed Responses	4	8	12	16	20
Observed Response Rate	4/40 (10.0%)	8/40 (20.0%)	12/40 (30.0%)	16/40 (40.0%)	20/40 (50.0%)
95% exact CI (%)	(2.8, 23.7)	(9.1, 35.6)	(16.6, 46.5)	(24.9, 56.7)	(33.8, 66.2)

A sample size of 40 can also detect, with more than 87% probability, a safety event that occurs at an incident rate of 5%.

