7.4.1 Analysis of Objective Response Rate and Disease Control Rate

One of the objectives of the study is to estimate the ORR per Investigator among all treated subjects.

The number and percentage of subjects in each category of BOR per Investigator (complete response [CR], partial response [PR], stable disease [SD], progressive disease [PD], or unable to determine [UTD]) will be presented. Estimates of response rate and disease control rate, along with its exact two-sided 95% CI by Clopper and Pearson³ will be presented.

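### The stated ORR power at n = 40 (79.8% and 83.7%) does not belong to the planned Clopper-Pearson rule, whose exact power is 70.0% and 78.9%

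*Protocol*

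**What the plan says.** Protocol 10.1 plans 40 participants per cohort. It sets an ORR above 10% as of clinical interest in TNBC and PAC, and above 20% in NSCLC. It then gives two power statements at a two-sided alpha of 5%:

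- for a true ORR of 25%, "40 participants in each tumor type can provide approximately 79.8% power to reject the null hypothesis that the ORR is 10"%;
- for a true ORR of 40%, "40 participants in each tumor type can provide approximately 83.7% power to reject the null hypothesis that the ORR is 20"%.

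Neither statement names a test. The section goes on to Clopper-Pearson intervals and gives the counts from which the lower 95% bound clears the reference rate: "At observed more than or equal to 9 responders" for 10% and "At observed more than or equal to 14 responders" for 20%. Table 10.1-1 lists the interval at 8/40 as (9.1, 35.6).

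SAP 5 repeats both power figures and both thresholds (for the 20% case, "If at least 14 responses are observed").

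The planned ORR analysis is exact in both documents. Protocol 10.3.1 says ORR "will be computed in each cohort along with the exact 95% CI using Clopper-Pearson method". SAP 7.4.1 presents the response rate "along with its exact two-sided 95% CI by Clopper and Pearson". SAP 7.4 rules out p-values. Protocol 10.1 and SAP 5 also state that the sample size was not derived from a power calculation.

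**The concern.** With no p-values and no other interval, the only planned way to reject an ORR of 10% or 20% is for the Clopper-Pearson lower bound to exceed it. A reader will therefore take 79.8% and 83.7% as the chance of that outcome, especially as the matching thresholds follow in the same section. If the figures belong to a different test, the chance that a truly active cohort clears its reference rate is overstated. Anyone interpreting a cohort that fails to exclude 10% would then assume a smaller risk of a false negative than the design carries.

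**Working it through.** **Inputs** (Protocol 10.1, SAP 5): n = 40; p0 = 10% against p1 = 25% (TNBC, PAC); p0 = 20% against p1 = 40% (NSCLC); two-sided alpha 5%, so z = 1.96.

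**1. Reproduce the printed power.** The uncorrected one-sample normal approximation is

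power = Φ[ (p1 − p0 − 1.96·√(p0(1 − p0)/n)) / √(p1(1 − p1)/n) ].

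- 10% v 25%: (0.15 − 1.96 × 0.04743) / 0.06847 = 0.833, and Φ = 0.7976.
- 20% v 40%: (0.20 − 1.96 × 0.06325) / 0.07746 = 0.982, and Φ = 0.8369.

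These are the printed 79.8% and 83.7%. Other common approximations do not give them: with continuity correction 74.2% and 79.4%, arcsine 72.3% and 79.9%, Wald (alternative variance only) 59.1% and 73.3%.

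**2. Check the printed thresholds.** The Clopper-Pearson lower bound for r responders is the 2.5% quantile of Beta(r, n − r + 1).

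| Responders | Lower bound | Excludes |
|---|---|---|
| 8/40 | 9.05% | not 10% |
| 9/40 | 10.84% | 10% |
| 13/40 | 18.57% | not 20% |
| 14/40 | 20.63% | 20% |

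The thresholds 9 and 14 are correct.

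**3. Exact power of those thresholds.** With X ~ Binomial(40, p):

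| Rule | Error at p0 (one-sided) | Exact power at p1 | Printed power | Gap |
|---|---|---|---|---|
| X ≥ 9 (10% v 25%) | 1.55% | 70.0% | 79.8% | 9.8 points |
| X ≥ 14 (20% v 40%) | 1.94% | 78.9% | 83.7% | 4.8 points |

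**4. Can any cut-off at n = 40 give the printed power?** No. For 10% v 25%, power is 81.8% at X ≥ 8 and 70.0% at X ≥ 9. For 20% v 40%, it is 87.1% at X ≥ 13 and 78.9% at X ≥ 14. The printed values fall between attainable ones.

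**5. What the z-test would do.** Its critical counts are 40 × 0.10 + 1.96·√(40 × 0.10 × 0.90) = 7.72 and 40 × 0.20 + 1.96·√(40 × 0.20 × 0.80) = 12.96. It therefore rejects from 8 and from 13, with one-sided error 4.2% and 4.3%, against 2.5% nominal. At 8/40 it rejects 10%, while Table 10.1-1 gives an interval from 9.1%, which does not.

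**6. Are the plan's other probabilities exact?** Yes. In Protocol 10.3.4, "If the true ORR is 10%, the probability of stopping the cohort is 68"%, and P(X ≤ 2 | 20, 0.10) = 67.7%. The 9% for a true ORR of 25% is P(X ≤ 2 | 20, 0.25) = 9.1%. The detection probability of more than 87% for a 5% safety event is 1 − 0.95^40 = 87.1%. Only the two power figures use an approximation.

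**The case against.** The printed numbers are not a slip in calculation. They reproduce to the printed decimal under a standard formula, the text says approximately, and the power sentences come before the interval, which is introduced as a statement of precision. On this reading they describe a different, unnamed test. Nothing operational rests on them either: the sample size is declared not power-based, ORR is secondary, clinical interest is not tied to 9/40 or 14/40, the futility look has its own correct probabilities, and enrolment is closed. The NSCLC figure has no remaining use, because SAP Schedule of Analyses reports that the combination was discontinued before 20 patients had been treated in that cohort.

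Most of this stands, and it limits the weight of the point. The defect is a mismatch of method, and its practical side is confined to TNBC and PAC. It does not remove the defect. Neither document plans a z-test, so the power sentences describe a property that the planned analysis lacks. A gap of 9.8 points is not covered by an approximation quoted to one decimal.

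**Conclusion.** The concern holds. For the planned exact interval at n = 40, the probability of excluding 10% when the true ORR is 25% is 70.0%, so the miss risk is 30.0%, where the text implies 20.2% (100 − 79.8). The probability of excluding 20% when the true ORR is 40% is 78.9%, a miss risk of 21.1% where 16.3% (100 − 83.7) is implied.

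These figures assume exactly 40 treated participants, independent binomial responses and, like the printed ones, no allowance for stopping at the futility look. They move with cohort size: for 10% v 25% the threshold is still 9 responders at 39 and 41 participants, with exact power 66.9% and 73.0%.

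The matter should be corrected, but its consequences are small. No sample size, analysis or decision rule in the plan depends on it. It bears mainly on how a TNBC or PAC interval that fails to exclude 10% is read in the final report.

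**What to change.** In Protocol 10.1 and SAP 5, replace the two power sentences with text to this effect:

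> With 40 treated participants, the two-sided 95% Clopper-Pearson interval lies entirely above 10% with probability 70.0% if the true ORR is 25% (9 or more responders), and entirely above 20% with probability 78.9% if the true ORR is 40% (14 or more responders). These are exact binomial probabilities at the planned cohort size.

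If the protocol is not to be reissued, correct the SAP and carry the exact figures into the synoptic report. The minimum acceptable alternative is to name the normal approximation and say that it is not the planned interval rule.

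The cost is two sentences per document and less favourable figures, both now below 80%. It needs no extra participants, no new data and no change to any analysis.

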## 10.2 Populations for Analyses

For purposes of analysis, the following populations are defined:

Population	Description
Enrolled	All participants who sign informed consent
All Treated	All enrolled participants who received at least one dose of study drug. This will be both efficacy and safety population.
Safety	All treated participants who received at least one dose of study treatment. Participants will be included in the treatment group that they actually received
Pharmacokinetic Participants	All participants who receive at least one dose of study drug and have available serum concentration data
Immunogenicity Participants	All treated participants with baseline and at least one post-baseline immunogenicity assessment for nivolumab or daratumumab.

## 10.3 Statistical Analyses

The statistical analysis plan will be developed and finalized before database lock and will describe the selection of participants to be included in the analyses, and procedures for accounting for missing, unused, and spurious data. Below is a summary of planned statistical analyses of the primary and secondary endpoints.

### 10.3.1 Efficacy Analyses

Endpoint	Statistical Analysis Methods
Primary	NA
Secondary	
ORR as defined as proportion of participants who achieved a best overall response (BOR) of CR or PR before taking any subsequent anti-cancer therapy, will be computed in each cohort along with the exact 95% CI using Clopper-Pearson method.
 
BOR is defined as the best response designation recorded between the date of first dose and the date of the initial objectively documented tumor progression per investigator assessment using RECIST 1.1 criteria or the date of subsequent therapy, whichever occurs first
 
Duration of response (or complete response) in each cohort will be estimated using KM product-limit method for participants who achieve PR or CR (or CR only). Median values along with two-sided 95% CI will be calculated.
 
Investigator-assessed progression free survival (PFS) is defined as the time from first dosing date to the date of the first documented tumor progression, as determined by investigators (per RECIST 1.1), or death due to any cause. Participants who die without a reported progression will be considered to have progressed on the date of their death. Participants who did not progress or die will be censored on the date of their last tumor assessment. Participants who did not have any on study assessments and did not die will be censored on the randomization date. A participant who initiates a subsequent anti-cancer therapy will be censored on the date of last tumor assessment prior or on the start date of their subsequent anti-cancer therapy.
 
The PFS curve, median and PFS rate at appropriate time points for each cohort will be estimated using the Kaplan-Meier product-limit method. Two sided, 95% confidence intervals for median PFS will be computed by Brookmeyer and Crowley method. A two-sided, 95% confidence interval for the PFS rates will be computed by Greenwood method for variance derivation and on log-log transformation applied on the survivor function S(t).

